1. USE OF THE STUDY DRUG: ANGAL/ANTI-ANGIN® FORMULA

No. of administration	Specify the time of administration	Did you experience a pain in your throat (before the use of spray)?	Complaints/Notes
1	HH:MM	YES / NO	
2	HH:MM	YES / NO	
3	HH:MM	YES / NO	
4	HH:MM	YES / NO	
5	HH:MM	YES / NO	
6	HH:MM	YES / NO	
7	HH:MM	YES / NO	
8	HH:MM	YES / NO	
0	HH:MM	YES / NO	
10	HH:MM	YES / NO	

2. BODY TEMPERATURE

	Specify the time of	RESULT
	measurement	OF MEASUREMENT
MORNING	HH:MM	°C
DAY	HH:MM	°C
EVENING	HH:MM	°C
Additionally	HH:MM	°C
Additionally	HH:MM	°C
Additionally	HH:MM	°C

3. COURSE OF THE DISEASE

	1 .	Based on your subjective evaluation of the disease symptoms, can you say	
		that you have improved so much that you do not need to use the spray	
		anymore?	
MORNING	HH:MM	YES / NO	
DAY	HH:MM	YES / NO	
EVENING	HH:MM	YES / NO	

TE_003_ANG_LSP	THE PATIENT'S DIARY	PATIENT No

DAY 2: DD/MM/YYYY

1. USE OF THE STUDY DRUG: ANGAL/ANTI-ANGIN® FORMULA

No. of administration	Specify the time of administration	Did you experience a pain in your throat (before the use of spray)?	Complaints/Notes
1	HH:MM	YES / NO	
2	HH:MM	YES / NO	
3	HH:MM	YES / NO	
4	HH:MM	YES / NO	
5	HH:MM	YES / NO	
6	HH:MM	YES / NO	
7	HH:MM	YES / NO	
8	HH:MM	YES / NO	
0	HH:MM	YES / NO	
10	HH:MM	YES / NO	

2. BODY TEMPERATURE

	Specify the time of	RESULT
	measurement	OF MEASUREMENT
MORNING	HH:MM	°C
DAY	HH:MM	°C
EVENING	HH:MM	°C
Additionally	HH:MM	°C
Additionally	HH:MM	°C
Additionally	HH:MM	°C

3. COURSE OF THE DISEASE

	ı v	Based on your subjective evaluation of the disease symptoms, can you say that you have improved so much that you do not need to use the spray anymore?
MORNING	HH:MM	YES / NO
DAY	HH:MM	YES / NO
EVENING	HH:MM	YES / NO

TE_003_ANG_LSP	THE PATIENT'S DIARY	PATIENT No

DAY 3: DD/MM/YYYY

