4.1.1.2 Additional efficacy endpoints

The secondary outcome measures in both therapy groups to compare the therapeutic efficacy of the study drug and comparator drug were:

- The frequency of ≥50% total score reduction according to the TSS questionnaire completed by the Investigator as compared to the baseline in both Angal and ANTI-ANGIN® FORMULA groups at Visit 2 (Day 4).
- Total score reduction according to the TSS questionnaire, as well as a reduction in the symptoms (sore throat, difficulty in swallowing, salivation, erythema, and fever) after a 3-day therapy, at Visit 2 (Day 4), as compared to the baseline total score.
- A period of time required for disease symptoms relief, determined according to the patient's diary (subjective patient's evaluation), but no more than 5 days during the trial—for patients who have achieved the corresponding outcome.
- A proportion (%) of patients who fully recovered by Day 4 in Group A and by Day 5 in Group B (the outcome of a disease according to the objective evaluation by the Investigator, the total score according to the TSS questionnaire <2).
- A change in the sore throat intensity by 100 mm VAS (visual analogue scale filled in by the patient) at the beginning, after 3 days of therapy, and at the end of treatment in both groups.

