9.1.3 Analysis of the secondary efficacy endpoints

- Frequency of ≥50% total score reduction according to the TSS questionnaire completed by the Investigator as compared to the baseline in both Angal S and ANTI-ANGIN® FORMULA groups at Visit 2 (Day 4).
- Total score reduction according to the TSS questionnaire, as well as a reduction in the symptoms (sore throat, difficulty in swallowing, salivation, erythema, and fever) after a 3-day therapy, at Visit 2 (Day 4), as compared to the baseline total score.
- A period of time required for disease symptoms relief, determined according to the patient's diary (subjective patient's evaluation), but no more than 5 days during the trial—for patients who have achieved the corresponding outcome.
- A proportion (%) of patients who fully recovered by Day 4 in Group A and by Day 5 in Group B (the outcome of a disease according to the objective evaluation by the Investigator, the total score according to the TSS questionnaire ≤2).
- A change in the sore throat intensity by 100 mm VAS (visual analogue scale filled in by the patient) at the beginning, after 3 days of therapy, and at the end of treatment in both groups.

The following statistical analysis methods are stipulated for the secondary efficacy endpoints:

• Frequency of ≥50% total score reduction by the TSS questionnaire completed by the Investigator relative to baseline in both Angal S and ANTI-ANGIN® FORMULA arms at Visit 2 (Day 4)—the response frequencies will be compared in each time point using the Fisher's exact test.

- Total score reduction by the TSS questionnaire, as well as reduction in symptoms (sore throat, difficulty in swallowing, salivation, erythema and fever) after 3-day therapy, at Visit 2 (Day 4), relative to baseline total score—the between-arm comparison will be carried out using the Mann–Whitney test due to non-symmetrical nature of the scores distribution in the TSS scale.
- A period of time required for the symptoms resolution defined by the patient's diary (subjective patient's evaluation), but not more than 5 days within the trial (for patients who achieved the relevant outcome)—the between-arm comparison will be carried out using t-test or the Mann–Whitney test depending on the distribution character. The survival will not be evaluated due to low duration of the trial.

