16.3 Appendix 3. The patient's diary

TE_003_ANG_LSP	THE PATIENT'S DIARY	PATIENT No

PATIENT COUNSELING INFORMATION

DEAR PATIENT,

This is a patient's diary. Please read the instructions for filling-in carefully. In case of any questions, feel free to ask the Investigator.

You are participating in a clinical trial of efficacy and safety of Angal S, spray with a menthol taste, compared to ANTI-ANGIN® FORMULA, a similar drug by action and composition, for therapy of acute, uncomplicated throat conditions.

The Investigator, based on your complaints and objective examination, has revealed that you have an acute, uncomplicated, infectious and inflammatory disease of the throat. One of the study drugs is prescribed to you to treat your condition: Angal S, spray with a menthol taste, or ANTI-ANGIN® FORMULA, spray. Both you and the Investigator know which drug you are taking because this is an open (unblinded) trial. The information you are going to note in this diary is very important for this trial; therefore, please enter the data without corrections.

Fill in the patient's diary every day. Encircle the answers YES or NO according to your opinion: YES. Take the diary with you when you visit the trial site. You will enter the following data:

- 1. Study drug use: every time when you use a spray dose, record the time and briefly describe your complaints at that moment. Specify if you had a pain in your throat before the spray use or not.
- 2. Measurement of body temperature: measure your body temperature 3 times a day or more frequently if needed. Specify a time and result of the measurement. Measure your body temperature in the axillary cavity, in a sitting position for 5 minutes. Please inform the Investigator on changes in your well-being.
- 3. Course of the disease: specify if you noted any changes based on your subjective evaluation of the disease signs.

If you feel worsening of state, increase of body temperature, aggravation of pain in your throat, contact the Investigator by the phone_____! If necessary, the Investigator will invite you for an unscheduled visit to the trial site for additional examination and therapy correction.

PRESCRIBING INFORMATION FOR THE STUDY DRUG

Angal, topical spray, one dose includes 3 to 5 consecutive presses on the actuator button, six to ten times per day, for not more than 4 days.

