ANTI-ANGIN® FORMULA, topical spray, one dose includes 1 to 2 consecutive presses on the actuator button, up to 6 times per day, for not more than 5 days.

TE_003_ANG_LSP	THE PATIENT'S DIARY	PATIENT No

DAY 1: DD/MM/YYYY

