1. USE OF THE STUDY DRUG: ANGAL/ANTI-ANGIN® FORMULA

No. of administration	Specify the time of administration	Did you experience a pain in your throat (before the use of spray)?	Complaints/Notes
1	HH:MM	YES / NO	
2	HH:MM	YES / NO	
3	HH:MM	YES / NO	
4	HH:MM	YES / NO	
5	HH:MM	YES / NO	
6	HH:MM	YES / NO	
7	HH:MM	YES / NO	
8	HH:MM	YES / NO	
0	HH:MM	YES / NO	
10	HH:MM	YES / NO	

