2.2 Secondary endpoints

- The frequency of ≥50% total score reduction according to the TSS questionnaire completed by the Investigator as compared to the baseline in both Angal S and ANTI-ANGIN® FORMULA groups at Visit 2 (Day 4).
- Total score reduction according to the TSS questionnaire, as well as a reduction in the symptoms (sore throat, difficulty in swallowing, salivation, erythema, and fever) after a 3-day therapy, at Visit 2 (Day 4), as compared to the baseline total score.
- A period of time required for disappearance of the disease symptoms, determined according to the patient's diary (subjective patient's evaluation), but no more than 5 days during the trial—for patients who have achieved the corresponding outcome.
- A proportion (%) of patients who fully recovered by Day 4 in Group A and by Day 5 in Group B (the outcome of a disease according to the objective evaluation by the Investigator, the total score according to the TSS questionnaire ≤ 2).
- A change in the sore throat intensity by 100 mm VAS (visual analogue scale filled in by the patient) at the beginning, after 3 days of therapy, and at the end of treatment in both groups.

VAS (visual analogue scale) to evaluate pharyngalgia severity:

The patient will fill in this scale at every visit to the trial site (Visits 1, 2, 3, where applicable). Calibrated scales 100 mm in length with the relevant measuring instruments will be provided for the clinical trial.

The patients should evaluate their pain severity according to VAS at every visit (if possible, before administration of the painkillers (if those are required) or the study drug/comparator drug).

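### The diary endpoint called time to symptom relief, resolution or disappearance rests on no diary item asking whether symptoms are gone; its apparent source asks whether the spray is still needed

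*Protocol*

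**What the plan says.** **Endpoint.** One secondary efficacy endpoint is a duration taken from the diary, and its name changes from place to place.

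- Protocol 4.1.1.2: "A period of time required for disease symptoms relief, determined according to the patient's diary (subjective patient's evaluation"). The synopsis, section 7.1 and the endpoint list in 9.1.3 also say relief.
- The methods paragraph of protocol 9.1.3: "A period of time required for the symptoms resolution defined by the patient", with the diary again as source. SAP 4.1.3 uses the same term, and the title of SAP Figure 4 speaks of resolution of disease signs.
- SAP 2.2: "A period of time required for disappearance of the disease symptoms".

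The arms are compared by t-test or Mann–Whitney test among patients who reached the outcome.

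**Diary (protocol Appendix 3).** There are three items per day.

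- Item 1 logs each spray use and asks: "Did you experience a pain in your throat (before the use of spray").
- Item 2 is body temperature.
- Item 3, course of the disease, is answered morning, day and evening. It asks the patient, on his or her subjective evaluation of the symptoms: "can you say that you have improved so much that you do not need to use the spray anymore". The question is the same on all five days.

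**Spray instructions in the diary.** For Angal S: "one dose includes 3 to 5 consecutive presses on the actuator button, six to ten times per day, for not more than 4 days". For ANTI-ANGIN FORMULA, 1 to 2 presses, "up to 6 times per day, for not more than 5 days".

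**The concern.** Improving enough to do without a spray is not the same event as being free of symptoms. If item 3 supplies the endpoint, a patient who still has mild pain can be counted as resolved, and nothing in the result would show it. Yet SAP 4.1.3 plans a between-arm test, and SAP Figure 4 a plot, under a title that says resolution.

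Two features add to the difficulty. Patients know their drug, and the regimen against which they judge further need is printed differently for the two arms. In addition, no derivation rule is written, so the analyst would have to choose, with data in hand, which YES counts.

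**Working it through.** The documents state no figure for this endpoint, so there is none to reproduce. The check sets the texts side by side.

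1. **Which item is the source?** The endpoint is described as the patient's subjective evaluation. Item 3 is the only diary item introduced that way, both in the diary instructions and in the question. Item 2 is temperature. Item 1 is a dosing log with one pain question. Item 3 is therefore the apparent source, although no text names it.

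2. **What does a YES to item 3 establish?** Measured against the three names: it fits *relief* fairly well, does not establish *resolution*, and does not establish *disappearance*. The threshold is no further need for the spray.

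3. **Could item 1 serve instead?** It covers throat pain only and is answered only when a spray is used. While spraying continues, a NO with a clock time is informative. Once spraying stops there are no entries, so it cannot reliably date the end of pain, and it says nothing about the other symptoms.

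4. **Is there a derivation rule?** Neither protocol 9.1.3 nor SAP 4.1.3 gives a source item, a start time, or a way to treat a YES followed by a NO. Item 3 is asked three times a day, so reversals can occur.

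5. **Is the reference point the same in both arms?** Presses per day from the diary instructions: Angal S 3 × 6 = 18 to 5 × 10 = 50; ANTI-ANGIN FORMULA at most 2 × 6 = 12, with no stated minimum. Protocol 6.3, however, says that both sprays are used when needed and that no lower compliance limit is assessed. SAP 3.2 excludes from the per-protocol set any patient who missed more than 3 doses, which presupposes scheduled dosing. These passages conflict and must be reconciled.

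6. **Is the observation window the same?** By protocol 4.2.4.2 and Table 1, Group A and recovered Group B patients return the diary at Visit 2 (Day 4); other Group B patients keep it to Day 5. A rule that a YES must not be followed by a NO would, if left uncapped, give those Group B patients extra opportunities for a NO.

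7. **Illustration of size.** Protocol 9.2 gives Day 4 counts for the active arm of the lozenge trial: 65 of 104 with no sore throat and 27 of 104 with mild sore throat. Let *s* be the assumed share of mild patients who would answer YES, and suppose all 65 pain-free patients do. The share of YES patients still in pain is 27*s* / (65 + 27*s*):
   - *s* = 10%: 2.7 / 67.7 = 4%
   - *s* = 50%: 13.5 / 78.5 = 17%
   - *s* = 100%: 27 / 92 = 29%

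**The case against.** The best defence is that the protocol's own definition is relief, and that item 3, which opens by anchoring the answer to the patient's view of the symptoms, is a reasonable measure of relief. SAP section 1 says no departures from the protocol are intended, so *disappearance* may be loose wording. This largely stands against the word *relief*. It does not rescue *resolution*, which is the protocol's own term in the methods paragraph of 9.1.3, or the title of Figure 4.

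A reader might go further and infer four things that the documents do not support.

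- *That the plan takes the endpoint from item 3.* This is a strong inference, but no text says it.
- *That a first YES would count even after a relapse.* Neither document contains that rule. The fault is that there is no rule.
- *That the arm instructions bias the comparison.* The when-needed statement in protocol 6.3 weakens the idea of a fixed minimum in Group A. A shift is possible, but its direction and size are unknown.
- *That 29% of resolved patients would still have pain.* That figure assumes every mild patient says YES. It also carries investigator-rated lozenge data over to a patient diary in a spray trial, and it says nothing about times or about the difference between arms.

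It is also fair to say that asking whether symptoms are gone is a stricter construct than relief. Hence the fix offers retitling as an alternative.

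**Conclusion.** The concern holds in a limited form. One secondary endpoint carries three names, no diary item measures absence of symptoms, the apparent source allows persisting pain, and the derivation is unspecified. As written, the endpoint cannot support a statement about time to symptom resolution or disappearance.

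The size cannot be fixed from the documents. The 4% to 29% range rests on the assumed YES shares and on transfer from another formulation.

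Severity is minor. SAP section 4 ties the non-inferiority conclusion to the primary endpoint alone and treats secondary variables as of research interest. The primary endpoint, the TSS endpoints and the VAS do not use this diary item.

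**What to change.** Choose one of two routes.

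- **Change the question.** On all five diary days, let item 3 ask whether the throat symptoms are gone, YES or NO, at the same three daily times and without reference to spray use.
- **Retitle, if the diaries are already in use.** In both the protocol and the SAP, including Figure 4, call the endpoint time to patient-reported no further need for the spray, and draw no conclusion on symptom resolution from it.

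On either route, use one name throughout, name item 3 as the source in protocol 9.1.3 and SAP 4.1.3, and define the event as the first YES not followed by a NO. Judge it over the same window in both arms, up to Visit 2 (Day 4). Separately, the diary instructions, protocol 6.3 and the missed-doses rule in SAP 3.2 must be reconciled.

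The cost is a diary amendment, which needs approval under protocol 11.2, or a wording change in both documents; retitling in the SAP alone would leave it at odds with the protocol. Events will be fewer or later than under a looser rule. Group B's Day 5 entries drop out of this endpoint, so its present 5-day limit must be changed to match.

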1. USE OF THE STUDY DRUG: ANGAL/ANTI-ANGIN® FORMULA

No. of administration	Specify the time of administration	Did you experience a pain in your throat (before the use of spray)?	Complaints/Notes
1	HH:MM	YES / NO	
2	HH:MM	YES / NO	
3	HH:MM	YES / NO	
4	HH:MM	YES / NO	
5	HH:MM	YES / NO	
6	HH:MM	YES / NO	
7	HH:MM	YES / NO	
8	HH:MM	YES / NO	
0	HH:MM	YES / NO	
10	HH:MM	YES / NO	

2. BODY TEMPERATURE

	Specify the time of	RESULT
	measurement	OF MEASUREMENT
MORNING	HH:MM	°C
DAY	HH:MM	°C
EVENING	HH:MM	°C
Additionally	HH:MM	°C
Additionally	HH:MM	°C
Additionally	HH:MM	°C

3. COURSE OF THE DISEASE

	ı v	Based on your subjective evaluation of the disease symptoms, can you say that you have improved so much that you do not need to use the spray anymore?
MORNING	HH:MM	YES / NO
DAY	HH:MM	YES / NO
EVENING	HH:MM	YES / NO

TE_003_ANG_LSP	THE PATIENT'S DIARY	PATIENT No

DAY 4: DD/MM/YYYY

1. USE OF THE STUDY DRUG: ANGAL/ANTI-ANGIN® FORMULA

No. of administration	Specify the time of administration	Did you experience a pain in your throat (before the use of spray)?	Complaints/Notes
1	HH:MM	YES / NO	
2	HH:MM	YES / NO	
3	HH:MM	YES / NO	
4	HH:MM	YES / NO	
5	HH:MM	YES / NO	
6	HH:MM	YES / NO	
7	HH:MM	YES / NO	
8	HH:MM	YES / NO	
0	HH:MM	YES / NO	
10	HH:MM	YES / NO	

2. BODY TEMPERATURE

	Specify the time of	RESULT
	measurement	OF MEASUREMENT
MORNING	HH:MM	°C
DAY	HH:MM	°C
EVENING	HH:MM	°C
Additionally	HH:MM	°C
Additionally	HH:MM	°C
Additionally	HH:MM	°C

3. COURSE OF THE DISEASE

	ı v	Based on your subjective evaluation of the disease symptoms, can you say that you have improved so much that you do not need to use the spray anymore?
MORNING	HH:MM	YES / NO
DAY	HH:MM	YES / NO
EVENING	HH:MM	YES / NO

TE_003_ANG_LSP	THE PATIENT'S DIARY	PATIENT No

DAY 5: DD/MM/YYYY

1. USE OF THE STUDY DRUG: ANGAL/ANTI-ANGIN® FORMULA

No. of administration	Specify the time of administration	Did you experience a pain in your throat (before the use of spray)?	Complaints/Notes
1	HH:MM	YES / NO	
2	HH:MM	YES / NO	
3	HH:MM	YES / NO	
4	HH:MM	YES / NO	
5	HH:MM	YES / NO	
6	HH:MM	YES / NO	
7	HH:MM	YES / NO	
8	HH:MM	YES / NO	
0	HH:MM	YES / NO	
10	HH:MM	YES / NO	

2. BODY TEMPERATURE

	Specify the time of	RESULT
	measurement	OF MEASUREMENT
MORNING	HH:MM	°C
DAY	HH:MM	°C
EVENING	HH:MM	°C
Additionally	HH:MM	°C
Additionally	HH:MM	°C
Additionally	HH:MM	°C

3. COURSE OF THE DISEASE

	ı v	Based on your subjective evaluation of the disease symptoms, can you say that you have improved so much that you do not need to use the spray	
		anymore?	
MORNING	HH:MM	YES / NO	
DAY	HH:MM	YES / NO	
EVENING	HH:MM	YES / NO	

[FE_003_ANG_LSP	THE PATIENT'S DIARY	PATIENT No.				
The patient was instructed on the diary completion	patient was instructed on the diary completion rules. The diary was given to the patient on Day 1 visit.					
Investigator (Full name/Signature)						
The diary was returned by the patient on time, acco	ding to the protocol. The data were entered correctly, all the cor	rections (if any) were discussed with the patient.				
Investigator (Full name/Signature)	Date					

16.4 Appendix 4. A visual analogue scale for sore throat evaluation

TE_003_ANG_LSP	THE VAS (VISUAL ANALOGUE SCALE) FOR SORE THROAT EVALUATION	PATIENT No.
VISIT: ☐ 1 ☐ 2 ☐ 3 ☐ unscheduled	I	
Date:		
D D / M M	Y Y Y Y	
Time:		
H H : M M		
of 0 (no pain) to 100 (the	ient: please evaluate the severity of pain worst pain one can ever imagine) and drint corresponding to the pain in your throa	aw a vertical line so that it crossed
No pain 0		The worst pain one 100 can ever imagine
Investigator		
(Full name/Signature)		
	Version 1.0 of September 29, 2016 in I	Russian
	* 6131011 1.0 01 September 27, 2010 III 1	CUSSIUII

This trial has been designed and conducted to evaluate non-inferiority of the therapeutic efficacy and safety of the study drug Angal S, topical spray [menthol] containing 0.5 mg of lidocaine hydrochloride and 2 mg of chlorhexidine digluconate per ml (Sandoz d.d., Slovenia), when compared to ANTI-ANGIN® FORMULA, topical metered spray giving 0.12 mg of tetracaine hydrochloride and 0.24 mg of chlorhexidine bigluconate per dose (OOO Valeant, Russia) in the treatment of patients with uncomplicated acute infectious and inflammatory diseases of the pharynx accompanied by a sore throat. The objective of this Phase III trial is to demonstrate the non-inferior therapeutic efficacy of the study drug as compared to the reference product.

This Statistical Analysis Plan was developed in accordance with the following documents:

- Guidelines for examination of medicinal products, Vol. 1. Federal State Budgetary Institution Scientific Center for Expert Evaluation of Medicinal Products under the Ministry of Health of the Russian Federation (eds. A.N. Mironov). Moscow: Grif and K, 2013.
- ICH harmonized tripartite guideline. Statistical principles for clinical trials (E9). Current Step 4 version dated 5 February 1998.
- GCP rules of the Eurasian Economic Union (a draft).

The objective of this Statistical Analysis Plan is more detailed, compared to Section 9 of the trial protocol, description of the main principles of the protocol-based statistical analysis, description of the primary and secondary endpoints analysis methods, as well as other data obtained during the trial.

This Plan stipulates for consistence of the scheduled and conducted statistical analysis to the trial protocol, including definition of the analysis data sets, transformations and calculations for the endpoints, observations quantity needed, etc. No changes in this Statistical Analysis Plan compared to the trial protocol are envisaged.

2. Trial endpoints

